8.4. Subject Replacement Criteria

Withdrawn subjects will not be replaced. If a substantial number of subjects are withdrawn from the study, the sponsor will evaluate the need for developing replacement criteria.

Randomized subjects who are withdrawn from the study may not re-enter. The subject number for a withdrawn subject will not be reassigned to another subject.

9. TREATMENTS

All IP should [REDACTED] at the site [REDACTED]
[REDACTED] The first dose will be administered at the study site.

Site personnel will instruct the subject to prime, then self-administer the IP by [REDACTED]
[REDACTED]

9.1. Identification of Investigational Product

The IP is defined as the spray delivery device containing PH94B or placebo.

PH94B [REDACTED]
[REDACTED]

The placebo is odorless and contains the identical excipients without PH94B.

PH94B and placebo are similar in appearance.

PH94B and placebo will be supplied [REDACTED]
[REDACTED]

The spray delivery device consists of an actuator and a 10-mL amber glass vial which contains 8 mL of IP.

Use of the i.n. route is essential given the site of action of PH94B on nasal sensory chemoreceptors (see Section 5.1).

PH94B and placebo will be supplied by [REDACTED]
[REDACTED]

9.2. Selection of Timing of Dose for Each Subject

Before initiation of treatment with the IP at Baseline (Visit 2), subjects will be trained by the Investigator or delegated staff in the proper technique for priming and self-administration of IP as outlined in the Study Manual.

The IP is to be delivered i.n. with the nozzle of the applicator positioned in the nasal vestibule and directed toward the midline (lower anterior part or nasal septum). To administer study medication, the actuator (pusher) should be depressed completely.

Prior to the use of a new IP vial, subjects will prime the spray pump by depressing the actuator 4 times. [REDACTED] After

the new IP vial has been primed for the first administration, only one priming spray is required for subsequent doses.

Subjects will be instructed to administer [REDACTED]

[REDACTED] The administration will be done during waking hours and the suggested spacing is at morning, noon, early evening, and bedtime.

[REDACTED] Placebo IP is one 100 µL spray per nostril for a total

of 200 µL. Study drug will be self-administered 4 times a day. The spacing between doses needs to be at least 2 hours.

9.3. Dose Adjustment Criteria

Dose adjustment is not allowed in this study.

9.4. Treatment Compliance

At Visits 2, 3, 4 and 5; subjects will be dispensed 2 vials of the appropriate IP. Subjects will take home the vials and store and use the IP at room temperature.

Before dispensing the vial(s) to a subject, the Investigator or study site staff will proceed as follows: (a) identify/mark the 2 vials as vial #1 and vial #2, (b) weigh the vials and record, registering the vial number and weight in the source document, c) instruct the subject to prime (4 sprays) the initial (#1) spray vial, and (d) have the subject self-administer the initial IP dose in the clinic office.

In the event a subject loses a vial of IP and requires a replacement vial to be dispensed, the Investigator or study coordinator must contact VistaGen Therapeutics, Inc. or its designee for replacement instructions. Study site staff will not be allowed to deviate from the dispensation order listed above for any reason.

The Investigator or study site staff will instruct the subject to return the used spray vials during the following visit to the clinic. At that time, the study personnel will weigh the returned vials and record the vial numbers and weights in the source document for compliance check.

Current and accurate inventory and dispensing records will be kept for all IP, and upon study completion, a final inventory of all clinical supplies will be compiled. All IP containers, whether empty or containing unused IP, will be returned per the sponsor's instructions from the clinical monitor. A copy of the Drug Receipt Form and the Drug Accountability Form will be retained in the Investigator's files.

Compliance with dosing instructions will be reasonably ascertained by weighing the vials as detailed in the Study Manual. The weight of the returned vials will be recorded in the source documents. Additional instructions will be provided in the Study Manual, including the estimated compliance calculation.

In the event the subject fails to return the IP vial(s) that was dispensed at the prior visit, site staff should ask the subject to return the vials to the site as soon as possible, preferably within 24 hours, but at the very least at the next scheduled study visit. The Investigator will also explicitly and thoroughly instruct the subject not to administer any further doses from the previously dispensed vial.

9.5. Method of Assigning Subjects to Treatment Groups

In this parallel group, randomized study, subjects who meet study entry criteria will be randomly assigned in a 1:1 ratio to PH94B or placebo. The randomization schedule will be computer generated using a permuted block algorithm and will randomly allocate IP to randomization numbers. The randomization numbers will be assigned sequentially through a central interactive web response system (IWRS) as subjects are entered into the study. The randomization schedule will be stratified by site. Study center will not be a blocking factor in the randomization schedule.

The randomization schedule will be prepared by Premier Research before the start of the study. No one involved in the study performance will have access to the randomization schedule before official unblinding of treatment assignment. No subject will be randomized into this study more than once.

9.6. Blinding and Unblinding Treatment Assignment

All subjects, investigators, and study personnel involved in the conduct of the study, including data management, will be blinded to treatment assignment with the exception of a specified unblinded statistician and a member of the Interactive Response Technology team from Premier Research who will have access to the randomization code. The unblinded study personnel will not participate in study procedures or data analysis prior to unblinding of the study data to all study-related personnel. If an interim analysis is to be conducted, then unblinded personnel who are not otherwise involved in the study will prepare the data for review.

Study personnel will make every effort to safeguard the integrity of the study blind to minimize bias in the conduct of the study. Treatment unblinding is discouraged if knowledge of the treatment assignment will not materially change the planned management of a medical emergency. Unblinding will be permitted in a medical emergency that requires immediate knowledge of the subject's treatment assignment. All IP containers will be provided with a code that will unblind the contents in an emergency (details are provided in the Study Manual).

Unblinding should be discussed in advance with the Medical Monitor, if possible. For emergency unblinding, study personnel will use the IWRS. If the Investigator is not able to discuss treatment unblinding in advance, then he/she must notify the Medical Monitor as soon as possible about the unblinding incident without revealing the subject's treatment assignment.

The Investigator or designee must record the date and reason for treatment unblinding on the appropriate eCRF for that subject. In all cases that are not emergencies, the Investigator must discuss the event with the Medical Monitor prior to unblinding the subject's treatment assignment.

If treatment assignment is unblinded for an individual subject, study personnel will be notified of that subject's treatment assignment without unblinding the treatment assignments for the remaining subjects in the study. Thus, the overall study blind will not be compromised. If a subject's treatment assignment is unblinded, he/she may or may not be asked to withdraw from the study. The Investigator will make this decision after consultation with the Medical Monitor.

Overall unblinding will take place at the end of the study only after database lock has been achieved.

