10. STUDY PROCEDURES

Subjects must provide written informed consent before any study-related procedures are initiated, including the cessation and taper of prohibited concomitant therapy.

For the timing of assessments and procedures throughout the study, refer to the schedule of events ([Table 2-1](#)). Throughout the study, every reasonable effort should be made by study personnel to follow the timing of assessments and procedures in the schedule of events for each subject. If a subject misses a study visit for any reason, the visit should be rescheduled as soon as possible. The same trained rater should complete the appropriate assessment with the subject for all visits.

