3.7. Blinding and Unblinding

This is a double-blind study throughout. All subjects, investigators, and study personnel involved in the conduct of the study, including data management, will be blinded to treatment assignment with the exception of a specified unblinded statistician and a member of the Interactive Response Technology team from Premier Research who will have access to the randomization code. Unblinded study personnel will not participate in study procedures or data analysis prior to the official unblinding of the study data to all study-related personnel. If an interim analysis is to be conducted, then unblinded personnel who are not otherwise involved in the study will prepare the data for review.

Study personnel will make every effort to safeguard the integrity of the study blind to minimize bias in the conduct of the study. Treatment unblinding is discouraged if knowledge of the treatment assignment will not materially change the planned management of a medical emergency. Unblinding will be permitted in a medical emergency that requires immediate knowledge of the subject's treatment assignment. All IP containers will be provided with a code that will unblind the contents in an emergency. Procedures for emergency unblinding will be outlined in the Study Procedures Manual for PH94B-CL029.

The Investigator or designee will record the date and reason for treatment unblinding on the appropriate electronic case report form (eCRF) for that subject. If treatment assignment is unblinded for an individual subject, study personnel will be notified of that subject's treatment assignment without unblinding the treatment assignments for the remaining subjects in the study. Thus, the overall study blind will not be compromised. Overall unblinding will take place at the end of the study only after database lock has been achieved.

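### Individual unblinding discloses the assignment to study personnel with no exception for efficacy raters, so some HAM-A and CGI-I ratings could be made unblinded

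*Protocol*

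**What the plan says.** - **Who is told.** Protocol 9.6: "If treatment assignment is unblinded for an individual subject, study personnel will be notified of that" subject's assignment, while the assignments of the remaining subjects stay concealed. SAP 3.7 carries the same sentence. Raters are not mentioned in either place.
- **What the Medical Monitor is told.** If prior discussion was not possible, the Investigator must "notify the Medical Monitor as soon as possible about the unblinding incident without revealing the subject's treatment assignment".
- **Whether the subject stays.** Protocol 9.6: "If a subject's treatment assignment is unblinded, he/she may or may not be asked to withdraw from the study". The Investigator decides after consulting the Medical Monitor.
- **Who rates.** Protocol 10.3.1.1 has trained personnel complete the HAM-A by structured interview. Protocol 7.2 has the Investigator and a trained observer perform the CGI-I. Protocol 10 adds: "The same trained rater should complete the appropriate assessment with the subject for all visits".
- **What enters the analysis.** Under SAP 6.1.4 and Table 3, subjects who discontinue attend an Early Termination visit whose Visit 6 measures are used for efficacy. SAP 6.1.4 sets the Visit 6 HAM-A to missing for loss to follow-up, inability to complete the Visit 6 assessments, or prohibited medication. Unblinding is not on that list.
- **What is recorded.** Protocol 9.6 puts the date and reason of unblinding on the eCRF, and the shell of SAP Listing 16.2.1.1 displays both.

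**The concern.** The primary endpoint is a clinician's judgement, and such a score can be influenced by knowing the treatment. Section 9.6 limits what the Medical Monitor learns to the fact of the incident, yet applies no such limit to the group that contains the endpoint raters. Staff who follow the text as written could tell a rater the assignment and then, under the same-rater rule, have that person score the remaining visits. Withdrawing the subject does not remove the problem, because the Early Termination rating is also used. Unblinding is not an intercurrent event in Protocol Table 13-1 or SAP Table 3, and neither sensitivity analysis in SAP 8.1.1 addresses it.

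**Working it through.** **1. The text.** The plan has no figure to reproduce here. The route to an unblinded rating is a chain of four statements:

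| Step | Source | Effect |
|---|---|---|
| Study personnel learn the assignment | Protocol 9.6, SAP 3.7 | The rater may be told |
| The subject may continue | Protocol 9.6 | Later visits are rated |
| Same rater at all visits | Protocol 10 | No change to a blinded rater |
| Early Termination data are used | SAP 6.1.4, Table 3 | A withdrawn subject's rating also counts |

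**2. Inputs for scale.** From the synopsis: 40 subjects randomized 1:1, so n = 20 per arm. From SAP 4.1: two-sided 0.05. Not in the readable documents, and therefore assumed: SD of HAM-A change 6 to 10 points; bias b of 3 to 10 points for each rating made unblinded. The calculation ignores any gain in precision from the baseline covariate.

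**3. Shift from m biased subjects in one arm:** m × b / 20.
- m = 1: 3/20 = 0.15 to 10/20 = 0.50 points.
- m = 3: 9/20 = 0.45 to 30/20 = 1.50 points.

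**4. Standard error of the difference:** SD × √(2/20).
- SD 6: 6 × 0.316 = 1.90.
- SD 10: 10 × 0.316 = 3.16.

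**5. Shift in standard errors, and two-sided type I error** under a normal approximation, Φ(s/SE − 1.96) + Φ(−s/SE − 1.96):

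| Events in one arm | Smallest (b = 3, SD 10) | Largest (b = 10, SD 6) |
|---|---|---|
| 1 | 0.15/3.16 = 0.05 SE; 0.050 | 0.50/1.90 = 0.26 SE; 0.058 |
| 3 | 0.45/3.16 = 0.14 SE; 0.052 | 1.50/1.90 = 0.79 SE; 0.124 |

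**6. CGI-I.** One responder classification changed in an arm of 20 moves that arm's proportion by 1/20 = 0.05.

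**7. Interaction with the missing-data rule.** If post-unblinding HAM-A scores were simply set to missing, 1 or 2 of 40 (0.025, 0.05) would fall under the group-mean imputation rule of SAP 6.1.4. With 3 of 40 (0.075), multiple imputation would be triggered. How the scores are excluded therefore has to be stated.

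**The case against.** The strongest counter-text is SAP 3.7: "Unblinded study personnel will not participate in study procedures or data analysis prior to the official unblinding". Protocol 9.6 has a similar sentence. In both places it follows directly on the unblinded statistician and the Interactive Response Technology team member, and it reads as a rule about them. If it did reach notified site staff, it would clash with the same-rater rule for a subject who stays in, and the passages would still need reconciling.

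Other points on that side have weight:
- Unblinding is discouraged unless it would change emergency management, and non-emergency cases need prior discussion with the Medical Monitor. Treatment lasts 4 weeks in 40 subjects. The synopsis reports no SAEs in over 200 subjects, although at shorter and less frequent exposure. Events should be rare. This stands.
- Section 9.6 places a general duty on study personnel to protect the blind, and procedural detail is left to a study manual that is not available here. The manual may narrow who is told, but the protocol and SAP wording does not.
- ITT analysis retains these subjects, and the eCRF and Listing 16.2.1.1 identify them. This is true, and it makes the fix cheap, but retaining and listing a score does not address bias in it.

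A reader might infer that the Medical Monitor rule and the notification rule contradict each other. The documents do not show that. The rules have different recipients, and the monitor's rule applies only where there was no prior discussion. It is an uneven application of need-to-know. A reader might also infer that one disclosed assignment makes later ones easier to guess. Protocol 9.5 and SAP 3.6 specify permuted blocks but give no block size, so this cannot be assessed.

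**Conclusion.** The point holds as a wording problem with a small expected effect. Following Protocol 9.6 and SAP 3.7 literally can put treatment-aware ratings into HAM-A and CGI-I, and the analysis plan has no provision for them. One event would shift the primary comparison by 0.05 to 0.26 standard errors on the assumed ranges. Only several events in the same arm, each with a large bias, would matter for the type I error. The case for a change rests on its low cost and on settling the handling before any event occurs.

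It would go too far to say that the notification has no benefit. Someone managing an emergency may need the assignment, and the Investigator must then decide on continuation. Nor is the primary endpoint exposed through CGI-I, which is a secondary endpoint. The point takes no position on whether an unblinded subject should remain in the study.

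**What to change.** **Protocol 9.6 and SAP 3.7.** State that study personnel are told only that an unblinding occurred. State that the assignment goes only to those managing the emergency and is not passed to the HAM-A rater or to any CGI rater who was not involved in the unblinding.

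**SAP 8.1.1 and 8.2.** Use the unblinding date already recorded on the eCRF to identify ratings made after unblinding. Pre-specify one sensitivity analysis of HAM-A and CGI-I that excludes them, run only if an event occurs. For HAM-A, specify direct exclusion in the manner of the complete case analysis in SAP 8.1.1.1, so that the 0.05 missing-data threshold does not determine the method. Because the protocol asks for the date and not the time, state how a rating on the day of unblinding is classed.

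**Cost.** Wording in two sections and one conditional analysis, with no new data collection. One limit remains: an Investigator who breaks the blind may also be a CGI rater. That rating is handled by the sensitivity analysis. Bringing in a replacement rater would break the same-rater rule and add between-rater variation, so it is not part of this proposal.

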9.7. Permitted and Prohibited Therapies

All concomitant medications used (including over-the-counter medications and herbal supplements) will be recorded in the source document and on the appropriate eCRF.

All medications taken by or administered to the subject during the month prior to Screening (Visit 1) should be recorded in the eCRF. With the exception of those noted in Section 8.2.2, all medications (prescription or over-the-counter) that were started prior to Screening (Visit 1) may be continued during the course of the trial. During the study, subjects should stay on stable doses of their usual allowable medication regimens. Medications for treatment of minor concurrent illnesses unrelated to AjDA that arise after Screening (Visit 1) may be allowed at the discretion of the Investigator, except for the prohibited therapies specified in the protocol.

To ensure that appropriate concomitant therapy is administered, it is essential that subjects be instructed not to take any medication (either self-administered non-prescription drugs or prescription therapy prescribed by another physician) without prior consultation with the Investigator. The Investigator should consider the acceptability of all concomitant medications not explicitly prohibited. Sites should contact the Medical Monitor when uncertain about the acceptability of concomitant medications. All concomitant medication taken during the study will be recorded on appropriate pages of the eCRF.

9.7.1 Permitted Therapies

With the exception of those noted in Section 9.7.2, all medications (prescription or over-the-counter) that were started prior to Screening (Visit 1) may be continued during the course of the trial. During the course of the study, subjects should stay on stable doses of their usual allowable medication regimens. Medications for treatment of minor concurrent illnesses that arise after Screening (Visit 1) may be allowed at the discretion of the Investigator, with the exception of the prohibited therapies specified in Section 9.7.2.

The use of eszopiclone, ramelteon, melatonin, zaleplon, zolpidem, low-dose doxepin or anti-histamines for the treatment of insomnia is permitted.

PH94B has no apparent pharmacodynamic drug interaction with phenylephrine and oxymetazoline in vitro. Investigator may allow concomitant use of over-the-counter nasal decongestants as needed. If the subject is taking nasal formulations, they should be spaced 15 minutes from IP administration.

9.7.2 Prohibited Therapies

With the exception of concomitant medications for the treatment of insomnia described in Section 9.7.1, no other psychotropic medication besides IP is permitted to be used by any subject between Screening (Visit 1) and Follow-up (Visit 7). Prohibited psychotropic medications include centrally acting medications used to treat pain and muscle spasms, such as gabapentin and cyclobenzaprine.

Prior use of PH94B is not permitted.

Where washout of prohibited medications is required before randomization, tapering rates are at the discretion of the Investigator and are to be determined on an individual basis, with consideration to subject state, dose, and known pharmacokinetics of the medication being discontinued. The subject must be consented before any tapering is started. If the washout of the anti-anxiety medications makes the subject clinically unstable, the Investigator has the discretion to not to proceed with the subject in the study.

